**Sing for Your Saunter**

**NIH R61AT010753**

**NCT04246476**

**August 1, 2023**

**Participants:**

People with Parkinson disease (PD) will be recruited through the Movement Disorders Clinic at Washington University in St. Louis School of Medicine and through flyers via the American Parkinson Disease Association. Age- and gender-matched controls will be recruited through the Washington University Older Adults Participant Pool and the Research Participant Registry. Additional recruitment occurred through advertisements, flyers, and social media.

Inclusion Criteria: 1) at least 30 years of age, 2) right-handed (criterion for MRI), 3) normal to corrected hearing, 4) able to walk for 10 continuous minutes independently, and 5) willing and able to provide informed consent. Additional inclusion criteria for people with PD included: 1) diagnosis of idiopathic, typical Parkinson disease according to the UK Brain Bank Criteria, 2) Hoehn & Yahr stages 2-3 (mild to moderate disease severity), 3) score of  $\geq 1$  on the Movement Disorders Society Unified Parkinson Disease Rating Scale – Part III – Motor Aspects (MDSUPDRS-III) item #10 indicating observable gait impairment; 4) a score of 1 or less on item # 7 on the New Freezing of Gait Questionnaire (nFOG-Q), indicating that the freezing episodes are not moderately or significantly disturbing to daily walking, 5) stable on all PD medications for at least 2 months prior to study entry.

Exclusion Criteria: 1) diagnosis of any other neurological condition; 2) significant cognitive impairment (i.e., Mini-Mental Status Examination (MMSE) score of  $<24$ ); 3) other medical conditions that might interfere with ability to safely participate.

This study will be approved by the Institutional Review Board (IRB) of Washington University in

St. Louis School of Medicine.

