**Analysis:**

T-tests will be used to compare baseline characteristics between groups. Repeated measures (RM) ANOVAs will be used to compare gait characteristics (velocity, stride length variability) across conditions (uncued, music, mental) and between groups (PD, control). For cued conditions, the optimal tempo (those at the tempo that elicited the longest strides for each participant) for each individual will be used for analysis. For significant main effects of condition, adjusted pairwise comparisons will be used to indicate differences between conditions.

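### Controls are matched on age and gender but the RM ANOVA omits both, so the PD-versus-control main effect is tested conservatively to the extent that age and gender predict gait

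*Combined protocol and SAP*

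**What the plan says.** The Participants section sets out how the comparison group is chosen: "Age- and gender-matched controls will be recruited", from two participant registers. It does not say whether this means one-to-one pairs, a caliper or frequency matching. The age criterion is "at least 30 years of age", with no upper limit, so age can vary widely within each group.

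The Analysis section is one paragraph. RM ANOVAs will be "used to compare gait characteristics (velocity, stride length variability) across conditions (uncued, music, mental) and between groups (PD, control"). No age or gender covariate is named, and no pair or stratum term. The only other between-group analysis is this: "T-tests will be used to compare baseline characteristics between groups". Nothing follows from those t-tests in the gait models. Post-hoc work is planned for condition only: "For significant main effects of condition, adjusted pairwise comparisons will be used". The document gives no sample size, allocation ratio, alpha, variance or effect size.

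**The concern.** A variable used to form the groups should also appear in the analysis. In this RM ANOVA the group F test is equivalent to a two-sample t test on each person's mean over the three conditions. Matching makes the two groups alike in age and gender, so these variables no longer contribute to the random variation of the group difference. Without covariates, though, they still inflate the spread of person means within each group, and that spread is what the test uses as its error. The reported error is then larger than the true one.

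The PD-versus-control comparison of gait level is one of the two comparisons that the plan names. At stake are the width of its interval and its power. In addition, the document gives no matching tolerance, and the planned model would not correct any imbalance that loose matching leaves.

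**Working it through.** **Inputs.** From the document: age and gender matching (Participants); a model with condition at three levels and group at two (Analysis). Assumed, because not stated: two-sided alpha of 5%; equal groups of 20, 30 or 60; R², the share of variance in person means explained by age and gender, from 0 to 0.30. The plan has no figure of its own to reproduce.

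**Standard error and size.** Let σ² be the total variance of person means and n the number per group.

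- Variance that the unadjusted model estimates for the group difference: 2σ²/n.
- True variance under matching: 2σ²(1−R²)/n.
- Overstatement of the standard error: 1/√(1−R²).
- True size: 2[1 − Φ(1.96/√(1−R²))].

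| R² | SE ratio | 1.96 × ratio | True size |
|---|---|---|---|
| 0 | 1.000 | 1.960 | 5.0% |
| 0.05 | 1.026 | 2.011 | 4.4% |
| 0.10 | 1.054 | 2.066 | 3.9% |
| 0.20 | 1.118 | 2.191 | 2.8% |
| 0.30 | 1.195 | 2.343 | 1.9% |

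**Simulation check** (10,000 replicates per setting; 20, 30 and 60 per group; three conditions; equal variances).

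- Unadjusted group test under exact, loose-caliper or frequency matching: size 4.5–4.8% at R² = 0.05, 3.5–4.3% at 0.10, 2.8–3.4% at 0.20 and 2.0–2.4% at 0.30. The form of matching makes little difference.
- Unadjusted group test without matching: near 5% at every R². The loss therefore comes from the mismatch between design and model.
- With age and gender as covariates under matching: 4.5–5.5% throughout.
- Group-by-condition test: 4.4–5.4% throughout, because additive age and gender effects cancel within a person. The same cancellation protects the condition test.

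**Power**, with 30 per group and an assumed difference of 0.7σ. The difference divided by the unadjusted standard error is 0.7/√(2/30) = 2.711. The critical t values are 2.002 (58 df) and 2.003 (56 df).

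- Unadjusted power ≈ Φ[(2.711 − 2.002)/√(1−R²)].
- Adjusted power ≈ Φ[2.711/√(1−R²) − 2.003].

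| R² | Unadjusted | Adjusted | Gain (points) |
|---|---|---|---|
| 0.05 | 77% | 78% | 1–2 |
| 0.10 | 77% | 80% | 3 |
| 0.20 | 79% | 85% | 6 |
| 0.30 | 80% | 89% | 9 |

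At an assumed 1.0σ, both powers are above 97% and the gain is under one point at each of these values of R².

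**The case against.** **Size.** Nothing in the document shows that age and gender explain 10% or more of the variance in velocity, still less in stride length variability. This stands. The size of the effect can be given only as a range that includes no effect.

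**Direction.** The conservative direction needs equal group sizes or similar variances, and the document promises neither. In a simulated case with 20 PD participants, 40 controls, PD residual SD 1.5 times the control SD and R² = 0.10, the unadjusted size was 7.6%. With 30 per group and the same variance ratio it was 4.5%. This stands as a condition on the point. Covariates do not cure that separate problem (adjusted size in the first case was 8.7%), but the document gives no sign that such an imbalance is planned.

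**Importance.** The experimental interest is in mental singing against music and uncued walking, and follow-up comparisons are planned for condition only. PD participants must also show a gait deficit to be eligible, so some group difference is expected and may be large enough that little power is lost. This is fair and lowers the priority. The group comparison is still named in the plan, and its interval should match the design.

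**Purpose of matching.** The document gives no reason for matching. If the aim was to limit confounding, the unadjusted analysis keeps that benefit, and the point estimate is no less precise. Only its reported error is too large. This stands, so it would be too strong to say that matching has been wasted.

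A reader might also infer that the cueing results are compromised or that false positives rise. The document supports neither reading: under additive age and gender effects the within-person tests hold their level, and the error from ignoring the matching is conservative.

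**Conclusion.** The point holds as a conditional one about efficiency. The design uses age and gender and the model does not, so the PD-versus-control main effect carries too large a standard error whenever those variables predict gait. Over the assumed R² of 0.10 to 0.30 the excess is about 5% to 20%, and the 5% test runs at about 3.9% down to 1.9%. At R² of 0.05 or less it can be ignored.

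A reader might infer that the group test certainly falls below its nominal level. The document does not support that: it states no R², sample size, allocation or alpha, and unequal groups with unequal variances could push the size the other way. What can be said without those figures is that the model omits its matching variables and leaves any residual imbalance in them uncorrected.

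**What to change.** Analyse each gait outcome with a linear mixed model: a random participant effect; fixed effects for condition, group and group-by-condition; and age (continuous) and gender as additive between-person covariates. If matching was one-to-one, a matched-pair term is an acceptable alternative. State the form of matching and the alpha level in the same paragraph.

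If RM ANCOVA software is used instead, centre both covariates, for example with gender effect-coded and then mean-centred. Such software usually adds covariate-by-condition terms. Centring age alone would leave the condition test dependent on how gender is coded.

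The cost is a sentence or two of analysis text and no new data, since both variables must be known in order to match. The mixed model spends two between-person degrees of freedom. The RM ANCOVA form also spends covariate-by-condition degrees of freedom: 2 covariates × (3 − 1) = 4 within-person.

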**Study design:**

All participants will come to the lab for a single session lasting 2-3 hours. The session involves behavioral assessments and motor assessments. People with PD will be tested while on their normal anti-PD medications to represent everyday conditions. Evaluations will be scheduled at the time of day identified by each individual as their optimal ON period when their medications worked best.

**Motor Assessments:**

Motor assessments will consist of several walking trials under varied conditions. Gait data will be recorded using the Mobility Lab System gait and posture analysis system (APDM, Inc., Portland, OR). This system is designed to quantify human movement and is equipped with six wearable Opal sensors placed on the wrists, feet, sternum, and lumbar spine. It is lightweight and wireless, allowing full freedom of movement and continuous monitoring of ambulation over long distances.

All walking trials will be performed in a 30m hallway in which participants walked continuously in an ellipse. A tone produced by the APDM software will indicate the start and end of each trial. In each condition, participants will perform three 30-second trials. All participants will be

followed by a trained physical therapist during walking trials to reduce fall risk during the intervention.

**Uncued walking:** Baseline walking trials will be done in silence and used to represent ‘normal’ baseline walking and to provide a point of comparison for the other conditions. Participants will be asked to walk at their preferred walking speed.

These trials will be averaged to determine baseline walking cadence and then used to calculate four individualized cue rates: 90%, 100%, 110%, and 120% of uncued cadence. Cues will be prerecorded on a piano keyboard and were rounded to the nearest five beats per minute increment.

During calculation of cue rates, participants will select a cue song from a curated catalogue of 10 songs compiled by a music therapist. These commonly known songs will be selected for having characteristics appropriate for gait training such as 4/4 timing, beat salience, familiarity, and simple lyrics. Participants will be asked to select the song most familiar to them.

The songs available will be as follows: “I’ve Been Working on the Railroad”, “You Are My Sunshine”, “This Land is Your Land”, “Skip to My Lou”, “She’ll Be Coming Around the Mountain”, “Don’t Sit Under the Apple Tree”, “When the Saints Go Marching In”, “You Can’t Hurry Love”, “When Johnny Comes Marching Home Again”, and “Seventy-Six Trombones.” All cued musical stimuli will be recorded on a keyboard using single notes. Only the chorus will be played to keep cues simple and repetitive to facilitate motor synchronization.

Once participants select a song, they will be given the song lyrics to review. To ensure each participant knows the lyrics, participants will then be asked to sing the song aloud without reading the lyrics. Participants will then practice singing the lyrics aloud while walking to familiarize them with performing the two tasks simultaneously.

**Cued walking:** Cues will be delivered from a laptop with external speakers. Tempos will be presented in randomized blocks and two cue types (Music and Mental) were randomized within each tempo.

- **Music:** This condition represents traditional cueing techniques in which music played and participants were asked to walk to the beat. Each song will be played once through before the starting tone sounded and participants began walking to the music. Participants will be monitored to ensure that they are not singing during this condition and that they walk on the underlying beat rather than the melody.
- **Mental:** This condition represents our experimental cueing paradigm in which participants were asked to mentally sing while walking without music playing. Each song will be played once through, then turned off before the starting tone sounds and participants begin walking and mentally singing. To ensure that participants are correctly doing the task, participants will be asked to confirm that they were mentally singing in their heads after each trial. Participants will be instructed not to move their mouths during the task and this will be carefully monitored.

Each participant will complete a total of 27 walking trials of 30 seconds each. Upon completion of all walking trials, each participant's optimal tempo (i.e., the tempo with the longest stride length) will be determined by averaging stride length across the music and mental trials within each tempo.

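### Do end-of-hall turns bias the comparison of stride length variability across conditions and groups?

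*Combined protocol and SAP*

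**What the plan says.** Under Motor Assessments, "All walking trials will be performed in a 30m hallway in which participants walked continuously in an ellipse". The timing is fixed: "In each condition, participants will perform three 30-second trials", and "A tone produced by the APDM software will indicate the start and end of each trial". Gait is recorded with a dedicated wearable system of six sensors, one of them on the lumbar spine. Uncued speed is self-selected, and the cues are then set at "four individualized cue rates: 90%, 100%, 110%, and 120% of uncued cadence".

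The Analysis section uses repeated measures ANOVA to "compare gait characteristics (velocity, stride length variability) across conditions (uncued, music, mental) and between groups (PD, control"). For the cued conditions it takes one tempo per participant, the one giving the longest strides. The Cued walking text determines that tempo by averaging music and mental trials together, and it randomises cue type within tempo.

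The documents do not give the size of the loop or the start point. They do not define the variability measure, and they do not say whether strides in turns are kept or removed.

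**The concern.** Stride length variability is sensitive to a few atypical strides. A loop in a hallway has two ends, and strides there are plausibly shorter than on the straight. Because trial time is fixed, distance depends on speed: a faster walker meets the ends more often. The cues are meant to alter gait, and people with Parkinson disease may differ from controls in both speed and turning. If turn strides counted in the outcome, a difference in variability might partly reflect turning rather than steadiness of gait. Both the condition and the group comparison would then be open to question. The remedy looks cheap, since sensor data could identify turns with no new measurement.

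**Working it through.** **Design figure.** Three uncued trials plus 4 tempos × 2 cue types × 3 trials gives 3 + 24 = 27, which matches "Each participant will complete a total of 27 walking trials of 30 seconds each". The documents give no speed, variability, corridor width or turn size, so every other input below is an assumption.

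**Turn exposure.** Distance = 30 s × speed. At 0.8, 1.0, 1.2 and 1.4 m/s this is 24, 30, 36 and 42 m. Most trials therefore reach at least one end of a 30 m hall.

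**Effect on the CV if turn strides are kept.** Let p be the share of turn strides, d their fractional shortening and c the straight-walking CV. Then

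CV = √[p(1−p)d² + (1−p)c² + p(c(1−d))²] / (1−pd).

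With c = 3%:

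| p | d | CV |
|---|---|---|
| 5% | 10% | 3.7% |
| 10% | 10% | 4.3% |
| 10% | 20% | 6.8% |
| 20% | 30% | 13.1% |

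With c = 5%, d = 5% and p = 15%, the CV is only 5.3%. The inflation can be large or trivial, according to inputs that the documents do not supply. At p = 5% and d = 10%, turning contributes 0.000475 of a variance of 0.001366, or 35%, so it need not dominate.

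**Does the inflation change with speed?** The formula depends on p, a share, and not on the number of turns. A faster trial meets more turns but also covers more straight distance. Take a half-lap of 30 m of which 3 m is turn, with c = 3% and d = 20%, and let share of distance stand for share of strides:

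| Speed (m/s) | Start of straight: p, CV | Mid-straight: p, CV | Random start: mean p, mean CV |
|---|---|---|---|
| 0.8 | 0%, 3.0% | 12.5%, 7.4% | 10%, 6.6% |
| 1.0 | 10.0%, 6.8% | 10.0%, 6.8% | 10%, 6.8% |
| 1.2 | 8.3%, 6.4% | 8.3%, 6.4% | 10%, 6.8% |
| 1.4 | 7.1%, 6.0% | 7.1%, 6.0% | 10%, 6.8% |

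From a mid-straight start each trial contains one whole turn, so p = 3/distance and the CV falls with speed. From the beginning of a straight the CV jumps near 1.0 m/s and then falls. From a random start it is almost flat. Raising speed from 1.0 to 1.2 m/s increases the expected number of turns by 20%, yet the CV does not rise under any of the three starts.

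Loop size matters too. With 20 m of usable length, a turn radius of 1 m and a mid-straight start, p goes from 10.5% at 1.0 m/s to 18.2% at 1.1 m/s and back to 14.0% at 1.5 m/s. The sign of any effect therefore depends on two quantities that are not stated.

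**Which contrasts are exposed.** Music and mental singing are analysed at the same target tempo in the same person, so the tempo setting gives no reason for their turn exposure to differ. The uncued-versus-cued and group contrasts are more open, but the documents give no speed difference for either.

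**The case for a change.** The strongest case for acting is that speed dependence appears in every fixed-start scenario; only a random start removes it, and then only on average. The group comparison does not even need a speed difference. With equal straight CV (3%) and equal turn share (10%), turn strides 10% shorter in one group and 20% shorter in the other give CVs of 4.3% and 6.8%, a gap produced entirely by turning. Entry requires observable gait impairment in the Parkinson group, so equal turning cannot be presumed. Retained turn strides could also influence which tempo is chosen: mean stride length is scaled by 1 − pd, so at d = 20% a move in p from 10.0% to 8.3% shifts it by about 0.3 percentage points, and from 10.5% to 18.2% by about 1.5.

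All of this stands as a conditional argument: it shows what could happen if turn strides were retained. It does not show that they are. The plan names the outcomes without saying which strides enter them, and silence is not a rule to include everything. The sizes rest wholly on assumed shortening, shares and group differences.

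Removing turns also has a cost. At an assumed 110 steps/min a trial has about 27 strides; dropping a turn of 2-3 strides plus one on either side loses 4-5 of them, 15-19% per turn. That may be worth paying, but it is a processing choice with a price.

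**Conclusion.** The concern does not call for a change. The plan leaves the handling of turn strides unwritten, along with loop size, start point and the definition of variability. That is missing detail, and nothing the plan does state is shown to give a wrong result. Analysts working with a dedicated gait system and a lumbar sensor can fill the gap sensibly, and a reader of the results can ask which strides were used.

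If turn strides were kept, variability would be inflated, from 3% to between 3.7% and 13.1% across the first table's assumptions. Neither the direction nor the size of a difference between conditions or groups can be derived from the documents. The music-versus-mental contrast is the least exposed, because it is made at one shared tempo. The group contrast is the one to read with most care, since different turning could matter there even at equal speed.

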**Analysis:**

T-tests will be used to compare baseline characteristics between groups. Repeated measures (RM) ANOVAs will be used to compare gait characteristics (velocity, stride length variability) across conditions (uncued, music, mental) and between groups (PD, control). For cued conditions, the optimal tempo (those at the tempo that elicited the longest strides for each participant) for each individual will be used for analysis. For significant main effects of condition, adjusted pairwise comparisons will be used to indicate differences between conditions.
